### 3.2 PRIMARY ENDPOINT

The primary endpoint is the proportion of subjects achieving culture conversion (3 consecutive monthly negative sputum cultures) by Month 6 in the LAI arm compared to multi-drug regimen alone.

### 3.3 SECONDARY ENDPOINTS

Secondary efficacy endpoints are:

1. Change in 6MWT distance at Month 6 in the LAI arm compared to multi-drug regimen alone
2. Proportion of subjects achieving culture conversion with durability at 3 months off treatment in the LAI arm compared to multi-drug regimen alone
3. Time to culture conversion in the LAI arm compared to multi-drug regimen alone at Month 6
4. Proportion of subjects achieving culture conversion with sustainability at the EOT in the LAI arm compared to multi-drug regimen alone
5. Change in 6MWT distance at EOT in the LAI arm compared to multi-drug regimen alone
6. Change from Baseline (Day 1) at Month 6 in the SGRQ.

### 3.4 EXPLORATORY ENDPOINTS

1. Change in 6MWT distance at Month 6 for converters versus non-converters in LAI arm
2. Change in 6MWT distance at Month 6 for converters versus non-converters for all subjects
3. Change in 6MWT distance at Month 6 for converters versus non-converters in the multi-drug regimen alone arm
4. Change in BMI at Month 6 in LAI arm compared to a multi-drug regimen alone
5. Change in 6MWT distance at Month 8 and 3 months off-treatment in the LAI arm compared to multi-drug regimen alone

Protocol Amendment #3 version: 22 February 2016

*This protocol is solely for the purpose of communicating information about the investigational drug between Inmed Incorporated and study personnel. Information is not to be reproduced, abstracted or used for sharing of information for any other purpose, whatsoever, except with the written permission of Inmed Incorporated.*

Confidential

6. Proportion of subjects achieving culture conversion with durability after 12 months off treatment (EOS) in the LAI arm compared to a multi-drug regimen alone
7. Change from Baseline (Day 1) at Month 6 in the SGRQ – Part 2 (Activities of Daily Living)
8. Change from Baseline (Day 1) at EOT in the EQ-5D-3L
9. Proportion of subjects who develop a new strain of MAC in the LAI arm compared to multi-drug regimen alone
10. Radiological changes in CT scan, within a sub-set of subjects, at EOT in the LAI arm compared to multi-drug regimen alone, where appropriate
11. Mortality at EOS

### **3.5 SCHEDULE OF EVENTS**

The schedule of events is presented in [Table 3-1](#). Detailed procedures and assessments performed at each scheduled study visit are presented in [Section 6](#).

Protocol Amendment #3 version: 22 February 2016

*This protocol is solely for the purpose of communicating information about the investigational drug between Inmed Incorporated and study personnel. Information is not to be reproduced, abstracted or used for sharing of information for any other purpose, whatsoever, except with the written permission of Inmed Incorporated.*

Confidential

**Table 3-1 Schedule of Events**

INS-212	Screening	TREATMENT PHASE											OFF-TREATMENT PHASE									
		Baseline	Month 1 a	Month 2 a	Month 3	Month 4	Month 5 a	Month 6	Month 8	Month 10	Month 12	Month 14	EOT up to Month 16	28 Day Safety Follow-Up	3 Month Safety Follow-Up	6 Month Safety Follow-Up	EOS (12 Month Safety Follow-Up)					
		(V1)	(V2)	(V3)	(V4)	(V5)	(V6)	(V7)	(V8)	(V9)	(V10)	(V11)	(V12)	(V13)	(V14)	(V15)	(V16)	(V17)				
Visit Window	Approximately -98 to -70 (10-14 weeks) b	Day 1	(±3)	(±3)	(±3)	(±3)	(±3)	(±3)	(±3)	(±3)	(±3)	(±3)	(±3)	(±5)	(±5)	(±5)	(±5)	(±5)	(±7)	(±7)	(±7)	(±7)
Informed consent	X	-	-	-	-	-	-	-	-	-	-	-	-	-	-	-	-	-	-	-	-	-
Pregnancy test c	X	X	X	X	X	X	X	X	X	-	X	-	X	-	-	-	-	-	-	-	-	-
ECG	X	-	-	-	-	-	-	-	-	-	-	-	X	-	-	-	-	-	-	-	-	-
SGRQ	-	X	-	-	X	-	-	X	X	-	X	-	X	-	-	X	-	X	-	-	-	-
EQ-5D-3L	-	X	-	-	X	-	-	X	X	-	X	-	X	-	-	X	-	X	-	-	-	-
Medical history	X	X	-	-	-	-	-	-	-	-	-	-	-	-	-	-	-	-	-	-	-	-
Physical examination	X	X			X	X		X	X	-	X	-	X	-	-	X	-	X	-	-	X	X
Vital signs and pulse oximetry	X	X d			X d	X d		X d	X d	-	X d	-	X	-	-	X	-	X	-	-	X	X
6 minute walk test e	-	X	-	-	-	X	-	X	X	-	-	-	X	-	-	X	-	X	-	-	-	-

Protocol Amendment #3 version: 22 February 2016

*This protocol is solely for the purpose of communicating information about the investigational drug between Insmid Incorporated and study personnel. Information is not to be reproduced, abstracted or used for sharing of information for any other purpose, whatsoever, except with the written permission of Insmid Incorporated.*

Confidential

INS-212	Screening	TREATMENT PHASE											OFF-TREATMENT PHASE									
		Baseline	Month 1 a	Month 2 a	Month 3	Month 4	Month 5 a	Month 6	Month 8	Month 10	Month 12	Month 14	EOT up to Month 16	28 Day Safety Follow-Up	3 Month Safety Follow-Up	6 Month Safety Follow-Up	EOS (12 Month Safety Follow-Up)					
		(V1)	(V2)	(V3)	(V4)	(V5)	(V6)	(V7)	(V8)	(V9)	(V10)	(V11)	(V12)	(V13)	(V14)	(V15)	(V16)	(V17)				
Visit Window	Approximately -98 to -70 (10-14 weeks) b	Day 1	(±3)	(±3)	(±3)	(±3)	(±3)	(±3)	(±3)	(±3)	(±3)	(±3)	(±3)	(±5)	(±5)	(±5)	(±5)	(±5)	(±7)	(±7)	(±7)	(±7)
Pulmonary Function Tests f (FEV 1 [L], FEF (25-75%) , FVC)	-	X	-	-	-	-	-	X	-	-	-	-	-	-	-	-	-	X	-	-	-	-
Audiology test	X g	-	-	X	-	-	X	-	-	X	-	X	-	X	-	-	-	-	-	-	-	-
Concomitant medications	X	X	X	X	X	X	X	X	X	X	X	X	X	X	X	X	X	X	X	X	X	X
Health Care Resource Utilization	-	X	X	X	X	X	X	X	X	-	X	-	X	-	-	-	-	-	-	-	-	-
AE assessment	-	X h	X	X	X	X	X	X	X	X	X	X	X	X	X	X	X	X	X	X	X	X
Sputum collection for microbiology	X	X	X	X	X	X	X	X	X	-	X	-	X	X	X	X	X	X	X	X	X	X
Chemistry	X	X	X	-	X	-	-	X	X	-	X	-	X	-	-	-	-	-	-	-	-	-
Hematology	X	X	X	-	X	-	-	X	X	-	X	-	X	-	-	-	-	-	-	-	-	-
Urinalysis	X	X	X	-	X	-	-	X	X	-	X	-	X	-	-	-	-	-	-	-	-	-

Protocol Amendment #3 version: 22 February 2016

*This protocol is solely for the purpose of communicating information about the investigational drug between Insmid Incorporated and study personnel. Information is not to be reproduced, abstracted or used for sharing of information for any other purpose, whatsoever, except with the written permission of Insmid Incorporated.*

Confidential

INS-212	Screening	TREATMENT PHASE											OFF-TREATMENT PHASE									
		Baseline	Month 1 a	Month 2 a	Month 3	Month 4	Month 5 a	Month 6	Month 8	Month 10	Month 12	Month 14	EOT up to Month 16	28 Day Safety Follow-Up	3 Month Safety Follow-Up	6 Month Safety Follow-Up	EOS (12 Month Safety Follow-Up)					
		(V1)	(V2)	(V3)	(V4)	(V5)	(V6)	(V7)	(V8)	(V9)	(V10)	(V11)	(V12)	(V13)	(V14)	(V15)	(V16)	(V17)				
Visit Window	Approximately -98 to -70 (10-14 weeks) b	Day 1	(±3)	(±3)	(±3)	(±3)	(±3)	(±3)	(±3)	(±3)	(±3)	(±3)	(±3)	(±5)	(±5)	(±5)	(±5)	(±5)	(±7)	(±7)	(±7)	(±7)
Serum for Biomarkers (CRP and IL-6)	-	X	-	-	-	-	-	X	-	-	-	-	X	-	-	-	-	-	-	-	-	-
Sub-Study: CT scan of chest i	-	X	-	-	-	-	-	-	-	-	-	-	X	-	-	-	-	-	-	-	-	-
Sub-Study: CT scan of chest (Japan)	See APPENDIX 5: JAPAN SPECIFIC CT SCAN SUB-STUDY																					
Sub-Set: Population PK sampling j (blood and sputum)	-	-	X	-	X	-	-	X	-	-	-	-	-	-	-	-	-	-	-	-	-	-
Sub-Set: Sputum only PK Collection	-	X	-	-	-	X	X	X	-	-	-	-	-	-	X	X	-	-	-	-	-	-
Sub-Study: Comprehensive PK sampling k (Japan)	X	X	-	X	-	-	X	-	-	-	-	-	-	-	-	-	-	-	-	-	-	-

Protocol Amendment #3 version: 22 February 2016

*This protocol is solely for the purpose of communicating information about the investigational drug between Insmmed Incorporated and study personnel. Information is not to be reproduced, abstracted or used for sharing of information for any other purpose, whatsoever, except with the written permission of Insmmed Incorporated.*

Confidential

INS-212	Screening	TREATMENT PHASE											OFF-TREATMENT PHASE							
		Baseline	Month 1 a	Month 2 a	Month 3	Month 4	Month 5 a	Month 6	Month 8	Month 10	Month 12	Month 14	EOT up to Month 16	28 Day Safety Follow-Up	3 Month Safety Follow-Up	6 Month Safety Follow-Up	EOS (12 Month Safety Follow-Up)			
		(V1)	(V2)	(V3)	(V4)	(V5)	(V6)	(V7)	(V8)	(V9)	(V10)	(V11)	(V12)	(V13)	(V14)	(V15)	(V16)	(V17)		
Visit Window	Approximately -98 to -70 (10-14 weeks) b	Day 1	(±3)	(±3)	(±3)	(±3)	(±3)	(±3)	(±3)	(±3)	(±3)	(±3)	(±5)	(±5)	(±5)	(±5)	(±5)	(±7)	(±7)	(±7)
Send sputum collection containers home	X	X	X	X	X	X	X	X	X	X	X	X	–	X	–	X	X	X	X	–
Administer study drug at site	–	X	X	X	X	X	X	X	X	X	X	X	–	X	–	–	–	–	–	–
Dispense study drug 	–	X	X	X	X	X	X	X	X	X	X	X	–	–	–	–	–	–	–	–
Collection of study drug vials	–	–	X	X	X	X	X	X	X	X	X	X	X	–	–	–	–	–	–	–
Start consent process for INS-312								X m												

Protocol Amendment #3 version: 22 February 2016

*This protocol is solely for the purpose of communicating information about the investigational drug between Insmmed Incorporated and study personnel. Information is not to be reproduced, abstracted or used for sharing of information for any other purpose, whatsoever, except with the written permission of Insmmed Incorporated.*

Confidential

**Note:** At visits where study drug is administered, all patient-reported outcomes, 6MWT, Physical Exam should be performed before study drug administration.

**Note:** Culture conversion is defined to occur when the first of 3 consecutive monthly sputum cultures are MAC negative. All NTM treatment will stop when a subject has completed 12 months of treatment starting from their first of 3 negative cultures when they were defined as a ‘converter’.

Abbreviations: AE, adverse event; CRP, C-reactive protein; CT, computed tomography; ECG, electrocardiogram; EOS, End of Study; EOT, End of Treatment; ED-5D-3L, EuroQol 5D; FEF(25-75%), forced expiratory flow at 25-75% of FVC; FEV1, forced expiratory volume in 1 second; FVC, forced vital capacity; PK, pharmacokinetic; SGRQ, St. George’s Respiratory Questionnaire.

- a Home Healthcare visits may be available for sites with IRB/EC approval to conduct Home Healthcare visits, and for qualifying subjects who may have difficulty attending clinic visits.
- b The Screening window allows time for sputum culture results, minimum inhibitory concentration (MIC) determination, and scheduling of Screening assessments. Any delay in obtaining microbiological results and MICs must be reported to the Sponsor immediately and documented within the study source documents. In the event that sputum culture results are not known by 8 weeks (Day -14), the Baseline (Day 1) visit should be scheduled as soon as possible in order to maintain the Screening window, and an extension of the Screening window to 14 weeks is allowed, if necessary. If sputum culture results are known prior to 8 weeks (Day -14), the Screening window of 10 weeks must be maintained.
- c Serum pregnancy testing will be performed on women of child bearing potential at Screening. A urine pregnancy test will be performed on women of child bearing potential at all other visits. Women not of child bearing potential are defined as postmenopausal (i.e., amenorrheic for at least 1 year), or surgically or naturally sterile.
- d Vital signs and pulse oximetry will be assessed both before and after dosing on visits where study drug is administered.
- e The 6MWT must be conducted by a site member who is blinded to the subject’s open-label treatment assignment.
- f The PFTs will be performed at sites with access to spirometers and trained personnel to perform spirometry tests. See [Section 7.2.4](#).
- g The Baseline audiology examination must be performed during Screening period or on Day 1 before study drug administration.
- h At Baseline (Day 1), AEs will be assessed only after study drug administration or first dose of multi-drug regimen. Any AE that has occurred prior to the first dose must be included in the subject’s medical history, including any AEs that occur within the Screening period.
- i Only for subjects who agreed to participate in the CT Scan sub-study. A prior chest CT scan may be used as a subject’s Baseline (Day 1) measurement if this CT scan was obtained within 6 months from the subject’s Baseline (Day 1) visit. Subjects will have their follow-up chest CT scan at the EOT visit provided the last chest CT scan was not obtained within the prior 6 months. High resolution CT scan is preferred, if available. Please refer to [APPENDIX 4](#) for additional details on the CT Scan sub-study.
- j Only for subjects who agreed to participate in the population PK sub-set (US and Japan only). Blood and sputum samples will be collected from 0 to 1 hours before and from 1 to 4 hours after study drug administration ([Section 7.4.1](#)).
- k Only for Japanese subjects from sites in Japan who agreed to participate in the comprehensive PK sub-study. Please refer to [APPENDIX 5](#) for additional details on the comprehensive PK sub-study.
- l Study drug will be dispensed to all subjects up to and including the Month 6 visit. At Month 8, subjects who are non-converters or experienced a relapse or recurrence after achieving culture conversion will exit the study at Month 8/EOT visit ([Section 3.1](#), [Section 4.6](#)). Subjects who remain in the study after Month 8 will receive study drug for 12 months beginning from the first of 3 negative cultures that defines culture conversion .
- m If Study INS-312 has been IRB/EC approved, start the ICF consent process at Month 6, in order to provide sufficient time for the subject to make an informed decision

Protocol Amendment #3 version: 22 February 2016

*This protocol is solely for the purpose of communicating information about the investigational drug between Insmad Incorporated and study personnel. Information is not to be reproduced, abstracted or used for sharing of information for any other purpose, whatsoever, except with the written permission of Insmad Incorporated.*

Confidential

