## 3 INVESTIGATIONAL PLAN

### 3.1 STUDY DESIGN

The Screening window allows time for sputum culture results, susceptibility by minimum inhibitory concentration (MIC) determination, and scheduling of Screening assessments. Any delay in obtaining microbiological results and MICs must be reported to the Sponsor immediately and documented within the study source documents. In the event that sputum culture results are not known by 8 weeks (Day -14), the Baseline (Day 1) visit should be scheduled as soon as possible in order to maintain the Screening window, and an extension of the Screening window to 14 weeks is allowed, if necessary. If sputum culture results are known prior to 8 weeks (Day -14), the Screening window of 10 weeks must be maintained. Once Screening assessments are complete and sputum culture results are known, eligible

Protocol Amendment #3 version: 22 February 2016

*This protocol is solely for the purpose of communicating information about the investigational drug between Insmid Incorporated and study personnel. Information is not to be reproduced, abstracted or used for sharing of information for any other purpose, whatsoever, except with the written permission of Insmid Incorporated.*

Confidential

subjects will be randomized 2:1 to LAI administered QD plus a multi-drug regimen or a multi-drug regimen alone. The primary endpoint will assess culture conversion by Month 6.

Sputum culture results will only be available to the site after the Month 6 sputum result is known, in time for the Month 8 visit. At Month 8 (-28 to +7 days), after all sputum culture results are known, up to and including Month 6, subjects will be assessed as converters or non-converters.

All converters will remain in Study INS-212 (Section 4.6). All converters who, after culture conversion, subsequently have MAC-positive sputum cultures in liquid broth media (agar negative) for 1 or 2 consecutive months only, will also remain in Study INS-212. These subjects will continue on their randomized treatment regimen until they complete a total of 12 months of treatment (EOT), starting from the first of 3 negative cultures that defines culture conversion. These subjects will return after the EOT visit for 28 day, 3, 6 and 12 months off-treatment follow-up visits. The 12 months off-treatment follow-up visit will be the end of study (EOS) visit. No NTM treatment will be administered during the off-treatment phase.

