#### **4.2 EXCLUSION CRITERIA**

A prospective patient with any of the following conditions must be excluded from this study:

1. patients with cystic fibrosis
2. patients whose MAC NTM infection is resistant to amikacin (as identified by MIC susceptibility  $>64 \mu\text{g/mL}$ )
3. patients who are not able to perform the 6MWT
4. positive pregnancy test or lactation at Screening. All women of child bearing potential will be tested. Women not of child bearing potential are defined as postmenopausal (i.e., amenorrheic for at least 1 year), or surgically or naturally sterile.
5. active pulmonary malignancy (primary or metastatic) or any malignancy requiring chemotherapy or radiation therapy within 1 year before Screening or anticipated during the study period
6. active allergic bronchopulmonary mycosis or any other condition requiring chronic systemic corticosteroids at a dose greater than the equivalent of 10 mg/day of prednisone within 3 months before Screening
7. active pulmonary tuberculosis requiring treatment at Screening
8. history of lung transplantation
9. initiation of chronic therapy (e.g., high dose ibuprofen, inhaled anti-inflammatory agents including steroids, low dose maintenance steroids, rhDNase) within 28 days before Day 1
10. administration of any investigational drug within 8 weeks before Screening

Protocol Amendment #3 version: 22 February 2016

*This protocol is solely for the purpose of communicating information about the investigational drug between Insmmed Incorporated and study personnel. Information is not to be reproduced, abstracted or used for sharing of information for any other purpose, whatsoever, except with the written permission of Insmmed Incorporated.*

11. prior exposure to LAI (including clinical study)
12. known hypersensitivity to aminoglycosides
13. use of inhaled or systemic aminoglycosides with activity against MAC (e.g., amikacin, kanamycin, or streptomycin) within 28 days before Day 1
14. acquired and primary immunodeficiency syndromes (e.g. HIV-positive patients regardless of CD4 counts)
15. significant (as determined by the investigator) hearing loss, vestibular dysfunction, neuromuscular weakness or a diagnosis of myasthenia gravis, where the potential risk of aminoglycoside toxicity outweighs the potential benefit
16. aspartate aminotransferase or alanine aminotransferase  $\geq 3$  times the upper limit of normal (ULN) or total bilirubin  $\geq 2$  times ULN at Screening

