## 6.2 BASELINE VISIT (DAY 1, VISIT 2)

All of the following should be performed or obtained within 70 days after Screening unless the results of the sputum culture analysis are delayed. In the event that sputum culture results are not known by 8 weeks (Day -14), the Baseline (Day 1) visit should be scheduled as soon as possible in order to maintain the Screening window, and an extension of the Screening window to 14 weeks is allowed, if necessary. If sputum culture results are known prior to 8 weeks (Day -14), the Screening window of 10 weeks must be maintained.

- administer SGRQ before study drug administration (see [Section 7.3.1](#))
- administer EQ-5D-3L before study drug administration (see [Section 7.3.2](#))
- collect information on healthcare resource utilization
- update medical history
- administer physical examination, including vital signs and pulse oximetry. Only vital signs and pulse oximetry will be assessed both before and after study drug administration (see [Section 7.2.2](#) and [Section 7.2.3](#))
- administer 6MWT (see [Section 7.2.1](#))

Protocol Amendment #3 version: 22 February 2016

*This protocol is solely for the purpose of communicating information about the investigational drug between Insmid Incorporated and study personnel. Information is not to be reproduced, abstracted or used for sharing of information for any other purpose, whatsoever, except with the written permission of Insmid Incorporated.*

- administer the pulmonary function test prior to study drug administration (see [Section 7.2.4](#))
- administer audiology test (may be administered either at the Screening or Baseline [Day 1] visit, not both; see [Section 7.2.9](#))
- obtain CT chest scan if part of CT Scan Sub-Study and has not been acquired within 6 months before Day 1 (see [Section 7.3.4](#), [APPENDIX 4](#))
- obtain CT chest scan if part of Japan specific CT Scan Sub-Study and has not been acquired within 6 months before Day 1 (see [APPENDIX 5](#))
- solicit concomitant medications (see [Section 7.2.8](#))
- assess AEs (see [Section 8](#))
- collect sputum specimen for microbiological assessment (see [Section 7.1.1](#))
- collect sputum specimen for sputum-only PK sub-set analyses (see [Section 7.4.1](#))
- collect blood or urine specimens for clinical chemistry, hematology, and urinalysis testing and, for women of child-bearing, a urine pregnancy test (see [Section 7.2.7](#))

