## **7.2.9 Audiology**

### **7.2.9.1 Methodology**

Audiology testing will be performed either at Screening or before administration of study drug at Baseline (Day 1), before study drug administration at Months 3, 6 and 12, and the end of treatment visit. Frequencies of 250, 500, 1000, 2000, 4000, and 8000 Hz will be evaluated for each ear using air conduction. If post-Baseline (Day 1) audiometry findings are an AE Grade 2 or higher (according to the Common Terminology Criteria for Adverse Events [CTCAE] Version 4.0 guideline), an additional audiometric evaluation should be conducted at the next scheduled visit.

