### **9.5.2 Per-protocol Population**

The per-protocol (PP) population is a subset of the ITT subjects who received at least 1 dose of either LAI plus a multi-drug regimen or a multi-drug regimen, met the inclusion/exclusion criteria, and did not have major protocol violations.

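### The baseline audiogram has to precede study drug but not randomisation, so the main evidence for exclusion 15 may first be seen with the open-label arm known

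*Protocol*

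**What the plan says.** **Timing of the test.** Footnote g of Table 3-1 reads "The Baseline audiology examination must be performed during Screening period or on Day 1 before study drug administration". Section 7.2.9.1 sets the same limit: "Audiology testing will be performed either at Screening or before administration of study drug at Baseline (Day 1"). Sections 6.1 and 6.2 add that the test "may be administered either at the Screening or Baseline [Day 1] visit, not both". A site that defers it to Day 1 therefore has no earlier scheduled audiogram.

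**The criterion.** Exclusion 15 (Section 4.2) covers "significant (as determined by the investigator) hearing loss", together with vestibular and neuromuscular conditions, "where the potential risk of aminoglycoside toxicity outweighs the potential benefit". It has no threshold and no time point. Exclusions 4, 7, 16, 17 and 18 are each tied to Screening.

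**Randomisation.** Section 3.1 randomises eligible subjects "Once Screening assessments are complete and sputum culture results are known". Section 3.6.4 also restricts randomisation to eligible subjects. Treatment is open-label (Sections 5.6 and 9.3). Appendix 4, Sub-Study Design, equates randomisation with Day 1.

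**Populations.** ITT is everyone randomised (9.5.1). Safety requires at least one dose (9.5.3). Per-protocol requires a dose and that subjects "met the inclusion/exclusion criteria, and did not have major protocol violations".

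**The concern.** An eligibility judgement should be closed before anyone at the site can know the arm. Here the timing limit on the most relevant measurement is tied to dosing. Dosing is the right limit for a safety reference value, but not for evidence that bears on an exclusion.

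The content of exclusion 15 makes the order matter. It weighs aminoglycoside risk, and the protocol assigns an aminoglycoside to one arm only. An investigator who sees an abnormal audiogram after an LAI allocation has a reason to act, and the same result after a control allocation gives little reason. At stake is balance on baseline hearing in the populations used for safety and per-protocol comparisons. Ototoxicity is an adverse event of special interest (Section 8.3).

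**Working it through.** **1. Can the audiogram follow allocation?**
- The audiogram may be done on Day 1 (footnote g, 6.1, 6.2, 7.2.9.1), and subjects are randomised on Day 1 (Appendix 4).
- Section 6.2 lists the Day 1 procedures without a randomisation step, so it fixes no order.
- Appendix 4, Sub-Study Procedures, has the sub-study CT scan done on Day 1 after randomisation. A Baseline procedure can therefore follow allocation on that day.
- Section 3.1 waits for Screening assessments. If a deferred audiogram is a Day 1 procedure, those can be complete without it. If it counts as a Screening assessment, the permission to do it on Day 1 sits badly with Section 3.1. Either way the passages need reconciling.

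**2. Is there a route from a late result to withdrawal?** Yes. Section 4.3, reason 7, and Section 5.12, item 1, let the investigator withdraw a subject or stop study drug on judgement. Section 7.2.9.2 sends pre-dose audiology findings to medical history and mentions no eligibility review.

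**3. The plan's own sample size (background; it is not in dispute).** Section 9.1 gives 20% against 5%, two-sided 0.05, continuity-corrected chi-square, 174 LAI and 87 control.

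Power = Φ[(d − 1.96·SE0)/SE1], where
- d = 0.15 − ½(1/174 + 1/87) = 0.1414
- pooled rate = (174 × 0.20 + 87 × 0.05)/261 = 0.15
- SE0 = √[0.15 × 0.85 × (1/174 + 1/87)] = 0.0469
- SE1 = √[0.20 × 0.80/174 + 0.05 × 0.95/87] = 0.0383

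This gives Φ(1.29) = 90.2%, in agreement with the stated 90% or more.

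**4. Effect on ITT under an assumed share.** Let h be the share of the LAI arm withdrawn after allocation and before dosing, all counted as non-converters. The LAI rate is 0.20 × (1 − h). The 351 planned randomisations split 2:1 give 234 and 117.

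| h (assumed) | LAI subjects withdrawn, of 234 | Similar controls kept, of 117 | LAI ITT rate | Power at 174/87 | Power at 234/117 |
|---|---|---|---|---|---|
| 0 | 0 | 0 | 20.0% | 90.2% | 97.4% |
| 2% | 5 | 2 | 19.6% | 88.7% | 96.8% |
| 5% | 12 | 6 | 19.0% | 86.2% | 95.7% |
| 10% | 23 | 12 | 18.0% | 81.1% | 92.9% |

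Exact power of a single-stratum Mantel-Haenszel test at 234/117, which has no continuity correction, falls from 98.7% to 98.4%, 97.7% and 96.0%.

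Outside Japan, Section 5.12 lets subjects who stop study drug stay to Month 8. If those withdrawn kept the control rate of 5%, the LAI rate at h = 10% would be 0.9 × 20% + 0.1 × 5% = 18.5%, so the table is the harsher case.

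**5. Effect on Safety and per-protocol.** LAI subjects who receive no dose leave both populations. The comparable controls, 2 to 12 of 117 under the same assumption, stay in Safety. They stay in per-protocol only if exclusion 15 is not applied to them. Treated LAI subjects would then include none of this group, against 2% to 10% of controls.

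**The case against.** The strongest reply is that the protocol already puts eligibility first. Sections 3.1, 3.6.4 and 9.3 randomise eligible subjects, and Section 4 requires that no exclusion applies. A site that formally decided exclusion 15 after allocation would be in breach. This stands. A reader might infer from footnote g that a compliant site may randomise, learn the arm and then apply the exclusion to LAI only. The text does not support that: exclusion 15 is worded for every prospective patient, and one-sided use is an inference about behaviour. What the reply does not do is put the audiogram ahead of allocation.

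Second, exclusion 15 names no audiogram and can be judged at Screening from history and examination, so the test may be only a safety reference value. That is a fair reading, but it leaves the investigator to face new, more direct evidence once the arm is known.

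Third, the consequences are limited. ITT keeps everyone, and any dilution works against LAI. The per-protocol rule binds both arms, so an ineligible control should leave as well. Hearing loss found before dosing is medical history, so retained controls affect the ototoxicity comparison only through later hearing events, and Section 9.7 plans summaries by arm without a test. All of this stands. A bias in favour of LAI is possible, but it is not shown.

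Fourth, the IWRS specification or site manuals may require confirmation of eligibility before assignment. They are not available here. The protocol text would still need to agree with them.

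**Conclusion.** The point holds as a gap in sequencing. The stated limit, before study drug, is the wrong one for a measurement that informs an eligibility judgement in an open-label trial, and it is not reconciled with the rule that only eligible subjects are randomised. The protocol does not build in an arm-dependent exclusion.

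The primary analysis is little affected. Even with 10% of LAI subjects withdrawn, the rate falls by 2 points, in the direction against LAI. The figures rest on an assumed 2% to 10% and on stacked worst cases: every affected subject's audiogram is deferred to Day 1 and done after allocation, every affected LAI subject is withdrawn undosed and counted as a non-converter, and no control is withdrawn.

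What remains is a modest risk to the comparability of the Safety population on baseline hearing, which matters for ototoxicity, and possibly of the per-protocol population. Its size cannot be estimated from the documents.

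**What to change.** Reconcile footnote g of Table 3-1 and Sections 6.1, 6.2 and 7.2.9.1 with Sections 3.1 and 3.6.4. State that, in both arms, the baseline audiogram is performed and the exclusion 15 decision documented before the subject is randomised in the IWRS. The test may still be done at Screening, or on Day 1 provided it comes before randomisation.

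No test, visit or subject is added, and no stated sample size changes. The Screening window of 10 to 14 weeks leaves room. The cost is slightly less freedom in booking audiology on Day 1.
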